4.1.2.2.2 MK-3682 PN021

MK-3682 PN021 is an ongoing Phase 2 randomized, multicenter, open-label trial to evaluate the safety and efficacy of MK-3682B for 16 weeks with RBV or 24 weeks without RBV in non-cirrhotic and compensated cirrhotic subjects with GT1 infection who have failed a previous DAA regimen. A subsequent cohort will enroll GT3 patients. Ninety-four GT1 patients have been randomized in this trial (80 [85%] GT1a; 14 [15%] GT1b). Patients had failed >8 weeks of ledipasvir/SOF (59 [63%]), ≤8 weeks of LDV/SOF (13 [14%]) or EBR/GZR (22 [23%]). Forty patients (43%) had cirrhosis. As of 21-July-2016, of the 94 enrolled subjects 2 have discontinued and 33 have completed treatment; all 92 subjects who have reached TW8 have achieved undetectable HCV RNA on treatment. To date, 22 subjects in the 16 week/RBV arm have reached FW4; all have achieved SVR₄ (Table 4).

Table 4 Current Efficacy Results for PN021

Proportion of Patients with HCV RNA <15 IU/mL [n/m, (%)]		
Treatment Week 4	Treatment Week 8	SVR4 (16 weeks/RBV)
85/92 (92%)	92/92 (100%)	22/22 (100%)

4.1.2.2.3 MK-3682 PN035

MK-3682 PN035 is an ongoing Phase 2 study that is currently evaluating the efficacy and safety profile of a 12-week regimen of MK-3682 450 mg + RZR 60 mg among subjects infected with GT1-6. As of 11-July-2016, 122 subjects have started treatment. All subjects have had rapid suppression of HCV viral loads and there have been no virologic breakthroughs on treatment.

4.2 Rationale

4.2.1 Rationale for the Trial and Selected Subject Population

Currently approved HCV IFN-free DAA regimens, such as LDV/SOF, SOF/VEL, ombitasvir/paritaprevir/dasabuvir/ritonavir+RBV, and EBR/GZR, have better efficacy, tolerability, and convenience than earlier therapies. However, they are not uniformly effective across the 6 HCV GTs. The most effective regimens are for GT1 HCV, which accounts for approximately 46% of infections worldwide [1]. Genotypes 2 and 3 HCV, the next most common GTs, were historically grouped together in treatment guidelines. However, recent studies have shown that infection with GT3, especially in subjects with cirrhosis, is more difficult to treat [25] [8] [9]. In addition, although GT5 and GT6 have a more limited geographic distribution than GT1-4, they predominate in certain regions of the world and represent an unmet medical need with limited clinical experience. In addition, even though several IFN-free combinations are now available for treatment of HCV, clinicians must still take into account the GT and even the subtype, as well as patterns of antiviral resistance in the choice of a regimen. The development of a single, uniform, and pangenotypic regimen that will be safe and effective in all patient populations would represent a substantial advance in the treatment of HCV infection by greatly simplifying treatment paradigms and reducing the need for pretreatment testing and on-treatment monitoring. The clinical potential of the combination of MK-3682 and RZR, both once-daily medications, is suggested by their non-overlapping viral targets, the pangenotypic *in vitro* potencies of both MK-3682 and RZR, the proven success of other HCV NIs in combination with other NS5A inhibitors, and the high efficacy rates from the investigational 3-drug regimen containing MK-3682, GZR, and RZR.

As previously described in Section 4.1.2, the investigational 3-drug regimen containing MK-3682, RZR, and GZR is being explored as a strategy to use 3 DAA agents, each directed at a different target of the hepatitis virus life cycle. As part of a comprehensive clinical development program, the combination of MK-3682 and RZR is currently being evaluated in MK-3682 PN035, an ongoing Phase 2 study characterizing the efficacy and safety profile of MK-3682 at a dose of 450 mg and RZR at a dose of 60 mg for 12 weeks duration. Dosing in PN035 is ongoing, and efficacy results are not yet available. PN041 is designed to explore

RZR at a dose of 180 mg as part of the 2-drug DAA regimen of MK-3682 (450 mg) and RZR (180 mg). The purpose of PN041 is to evaluate the use of a higher dose of RZR as a potential strategy to develop a highly efficacious pangenotypic DAA regimen for the treatment of chronic HCV. The rationale for dose selection is provided in Section 4.2.4.2.

4.2.2 Rationale for the Selected Subject Population

The rationale for the population selected for this trial is as follows:

- **Genotype:** The efficacy of the 2-drug regimen in subjects with chronic HCV-GT1-6 will be evaluated to allow for an initial assessment of the 2-drug combination regimen of MK-3682 and RZR as a pangenotypic therapy for HCV. The preclinical profiles of MK-3682 and RZR demonstrate high potency against GT1-6 *in vitro*. In addition, the preliminary data from Phase 2 studies of MK-3682/GZR/RZR demonstrate excellent tolerability and high efficacy of this 3-drug regimen when administered in GT1, GT2, and GT3. Taken together, these data support the clinical evaluation of the combination of MK-3682 and RZR as a pangenotypic therapy for HCV.

In preclinical *in vitro* experiments, MK-3682 and RZR were shown to have high potency against all GTs.

- The triphosphate of MK-3682, MK-3682-NTP, is a potent, pangenotypic inhibitor of HCV NS5B polymerase, with mean IC₅₀ values of 0.144 ± 0.011 μM (GT1a), 0.238 ± 0.024 μM (GT1b), 0.250 ± 0.005 μM (GT2a), 0.156 ± 0.012 μM (GT3a), 0.149 ± 0.016 μM (GT4a), 0.233 ± 0.003 μM (GT5a), and 0.097 ± 0.006 μM (GT6a).
- RZR is a potent, pangenotypic inhibitor of NS5A, with low EC₉₀ against GT1a (0.002 nM), GT1b (0.003 nM), GT2a (0.001 nM), GT2b (0.036 nM), GT3a (0.006 nM), GT4a (0.011 nM), GT5a (0.001 nM) and GT6 (0.004 nM) in replicon assays.
- **Treatment-Naïve:** TN subjects who have never received medical therapy for HCV and have no evidence of cirrhosis represent the largest proportion of the HCV-infected population worldwide. Historically, these subjects have had a high response rate to HCV DAA therapies.
- **Treatment-Experienced Subjects:** This study will also include subjects who have previously failed treatment with IFN-based therapies, because subjects who have failed prior interferon-based treatment are among the populations at highest need for effective HCV treatments. Although the efficacy rates in IFN-based TE populations have historically been lower than in TN populations, more recent IFN-free DAA therapies combining highly potent drugs have demonstrated high rates of SVR₁₂ in TE subjects that are comparable to those achieved in TN subjects [12] [15] [3] [22] [33] [25] [34]. Given the comparable SVR₁₂ rates observed following some all-oral DAA regimens in TE and TN subjects, TE subjects will be permitted to enroll in this study. As stated in Sections 2.1 and 4.2.3, this study includes duration modification rules to limit the potential for subjects to be at risk for virologic failure. Subjects who have failed prior DAA regimens will not be included in this study to allow further

evaluation of the efficacy of this 2-drug regimen in TN and PR TE subjects, some of whom will have baseline RAVs. The DAA failure population may have a higher prevalence of baseline RAVs so is best addressed at a later time.

- **Non-cirrhotic Subjects:** Non-cirrhotic subjects represent a large proportion of the HCV-infected population worldwide. Historically, these subjects have had a high response rate to HCV DAA therapies.
- **Compensated Cirrhotic Subjects:** Subjects with cirrhosis who are at increased risk for progression to decompensated cirrhosis and liver complications are one of the more challenging groups in need of new therapeutic approaches. Although the efficacy rates in cirrhotic populations have historically been lower than in non-cirrhotics, requiring longer treatment durations or the addition of RBV to achieve equivalent SVR₁₂ rates, more recent IFN-free DAA therapies combining highly potent drugs have demonstrated rates of SVR₁₂ in compensated cirrhotic subjects that are comparable with those achieved in non-cirrhotic subjects [4] [3] [25] [34]. Given the comparable SVR₁₂ rates observed following 12 weeks of all-oral IFN-free DAA regimens in non-cirrhotic and compensated cirrhotic subjects, including the 3-drug regimen of MK-3682/GZR/RZR in non-cirrhotic and compensated cirrhotic subjects, subjects with compensated cirrhosis will be permitted to enroll in this study. In addition, as stated in Sections 2.1, 4.2.3, and 5.11, this study includes limitations on the number of cirrhotics, stopping rules, and duration modification rules to limit the potential for subjects to be at risk for virologic failure. Subjects with advanced or decompensated cirrhosis will not be included in this study.
- **HIV Co-infected Subjects:** HIV co-infected subjects are included in this trial because HCV infection is a leading cause of morbidity and mortality among those with HIV-1 [35]. Compared to the general population, the overall prevalence of HCV infection is higher among those infected with HIV-1. In fact, one-fourth to one-third of subjects infected with HIV in the US and Europe are co-infected with HCV [36]. Compared to subjects infected with HCV alone, HIV/HCV co-infected subjects have higher baseline HCV viral loads (VLs) and more rapid progression of liver disease, including more rapid hepatic fibrosis as well as an increased risk of cirrhosis, end-stage liver disease, and hepatocellular carcinoma. Subjects with HIV/HCV co-infection are also more susceptible to developing anemia, and they may have more rapid progression to acquired immunodeficiency syndrome (AIDS) and AIDS-related death [29]. Recent DAA therapies have demonstrated rates of SVR₁₂ that are comparable with those achieved in HCV disease-matched mono-infected subjects. In particular, HIV subjects co-infected with HCV GT1 or GT4 had similarly high efficacy following EBR/GZR therapy in Phase 3 studies compared to those who were not HIV-infected [6]. Given the comparable SVR₁₂ rates observed following all-oral IFN-free DAA regimens in mono-infected and co-infected subjects, HIV/HCV co-infected subjects will be permitted to enroll in this study. A comprehensive set of drug-interaction trials has defined the antiretroviral therapies that can be co-administered with MK-3682, GZR, and RZR (Section 5.5).

4.2.3 Rationale for Study Design

The pangenotypic preclinical profiles of MK-3682 and RZR, as well as the preliminary efficacy results from the 3-drug, 8- and 12-week regimens of MK-3682/GZR/RZR in GT1, GT2, and GT3 support the proposed evaluation in this protocol of the safety and efficacy of MK-3682 + RZR in TN or prior IFN-based TE, non-cirrhotic and compensated cirrhotic GT1-, GT2-, GT3-, GT4-, GT-5, and GT-6-infected subjects. A treatment duration of 12 weeks for all GTs using the MK-3682 + RZR combination in this study is supported by the equipotent or superior *in vitro* potency profiles of MK-3682 and RZR (Section 4.2.2) compared to other compounds of the same classes, such as the approved NI/NS5A regimens of LDV/SOF and SOF/VEL, that have demonstrated high efficacy rates against GT1-6 after 12 weeks of treatment as 2-drug IFN-free DAA regimens. Ribavirin is not proposed to be evaluated in this trial given the high efficacy rates observed with other 2-drug all-oral DAA regimens without RBV, such as LDV/SOF and SOF/VEL, and the equipotent or superior *in vitro* potency profiles of MK-3682 and RZR compared to these regimens.

Since this is an estimation study, no comparator or placebo is used. No statistical comparisons are planned for efficacy and safety data. A target number of GT1-, GT2-, GT3-, and GT4-infected subjects are specified in order to provide sufficient confidence of the estimated treatment response rate in these GTs, since they are the most prevalent GTs globally. Since subjects with GT5 and GT6 are uncommon outside of certain geographic areas, the study will enroll approximately a stated number of subjects with the assumption that full enrollment of these GTs may not be reached.

Treatment allocation will pause after the first 50 subjects complete the TW4 visit. This will allow general safety and tolerability to be assessed after these first 50 subjects complete TW4, an assessment of 20% of the overall allocation target. The TW4 time point allows for steady state of drug to be achieved for ≥ 2 weeks. The criteria described in Section 5.11.1 provide a conservative approach to expanding treatment allocation to the subsequent 200 subjects. These criteria will allow the identification of safety concerns, while not allowing the trial to be stopped unnecessarily.

Treatment allocation may be stopped or paused at any time during the trial if certain criteria are met, as detailed in Section 5.11. If efficacy criteria for stopping enrollment/treatment allocation are met (Section 5.11.4), then no additional subjects of that particular GT will be allocated to treatment in the trial. In addition, the treatment regimen will be modified for all subjects of that GT still on treatment by extending the duration of treatment with MK-3682 + RZR to 16 weeks and adding RBV to the regimen.

4.2.4 Rationale for Dose Selection/Regimen

4.2.4.1 Dose Selection for MK-3682

The 450-mg dose of MK-3682 was chosen for the MK-3682B FDC regimen based on the dose-response analysis generated by monotherapy data from MK-3682 PN001, by the exposure data from the tablet formulation from MK-3682 PN003 and by dose ranging data from PN011 and PN012 Part A. This analysis suggests that the 450-mg dose of MK-3682 in the tablet formulation will be well on the plateau of the dose-response curve and would

provide improved protection against loss of efficacy than would the 300 mg of the tablet formulation, while still maintaining margins to preclinical safety exposures. Efficacy of the MK-3682 300 mg and 450 mg dose arms in GT3-infected subjects in PN012 Part A showed SVR₁₂ of 39/42 (93%) and 39/44 (89%), respectively. In GT2-infected subjects in MK-3682 PN011 Part A, slightly higher efficacy was observed in subjects on the 450-mg dose of MK-3682, with an SVR₁₂ rate of 77% (24/31) versus 70% (21/30) on the 300-mg dose. The highest efficacy in GT2-infected subjects was observed in the MK-3682 (450 mg)/GZR/RZR arm with an SVR₁₂ rate of 94% (15/16), supporting the selection of this regimen for Part B. In addition, the 450-mg dose of MK-3682 has demonstrated an acceptable safety profile when administered once daily for up to 24 weeks in Phase 2 studies, with no difference compared with the 300 mg dose. Therefore, 450 mg was selected as the dose to be evaluated in this protocol.

4.2.4.2 Dose Selection for RZR

Based on the available safety, tolerability, PK, and PD data, 180 mg and 60 mg doses of RZR, respectively, were chosen to be evaluated in combination with a 450 mg dose of MK-3682 in this protocol and in the ongoing PN035.

Preliminary PD data from RZR PN003 have demonstrated that 60 mg of RZR monotherapy for 5 days achieved $>3 \log_{10}$ mean maximal viral load reduction in HCV GT1-, GT2-, and GT3-infected subjects. Additionally, the efficacy was similar across doses of 10- to 60-mg doses. The mean maximum VL reduction was -3.82 in GT2 and -2.83 in GT3 following 10 mg of RZR for 5 days, and -3.03 in GT3 following 30 mg of RZR for 5 days. However, a less robust VL reduction ($-1.75 \log_{10}$ IU/mL) at a 120-mg dose was observed in GT3-infected subjects due to baseline or treatment-emergent RAVs in the 3 GT3-infected subjects. One subject had S62L/Y93H RAVs at baseline and a treatment-emergent maximal VL reduction of $-0.34 \log_{10}$ IU/mL; 1 subject had no detectable RAVs at baseline but had both S62L and Y93H treatment-emergent RAVs and a $-1.85 \log_{10}$ IU/mL VL reduction; and the third subject had an A30K RAV at baseline and a Y93H/Y treatment-emergent RAV and $-3.06 \log_{10}$ IU/mL VL reduction. The results from monotherapy study suggested that RZR at a dose of equal or greater than 10 mg is associated with a robust VL decline, but RZR monotherapy may not exhibit full efficacy against some GT3 RAVs and therefore supports the further evaluation of RZR at a dose equal to or greater than 10 mg in combination with other antiviral agents. For detailed information, please refer to the RZR IB.

The high efficacy rates from the Phase 2 studies of the 3-drug regimen containing MK-3682 450 mg, RZR 60 mg, and GZR 100 mg in GT1-, GT2, and GT3-infected subjects support the continued development of the MK-3682B regimen with a 60-mg dose of RZR. PN035 is currently being conducted to evaluate the 2-drug regimen of MK-3682 (450 mg) and RZR (60 mg).

Given that GZR is highly effective in GT1-infected subjects, it is possible that a higher dose of RZR may be needed to compensate for the removal of GZR in a 2-drug regimen. The current study (evaluating RZR 180 mg) is proposed to examine the dose response of RZR in combination with MK-3682 as a potential highly efficacious 2-drug regimen.

The higher dose of RZR selected for this trial, 180 mg, is supported by the preclinical safety margin and the predicted PK. RZR at the 60-mg dose has demonstrated excellent tolerability

when administered alone or as an MK-3682B FDC regimen in combination with MK-3682 and GZR (Section 4.1.2.2.1). The steady state exposures of RZR 180 mg in HCV subjects are anticipated to be 3- to 30-fold below the exposures achieved in preclinical safety assessment toxicity studies and ancillary pharmacology studies. In the thorough QT study (MK-8408 PN007), a suprathreshold dose of 600 mg RZR did not cause QTc prolongation and was generally well tolerated; there were no SAEs, deaths, or ECIs reported. This dose yielded a margin for maximum plasma concentration (C_{max}) of approximately 2.9-fold and AUC_{0-24} of approximately 2.3-fold relative to RZR steady state exposure at the 60-mg dose. Additionally, multiple doses of RZR were generally well tolerated after 100 mg once daily for 10 days in healthy subjects and 120 mg once daily for 5 days in HCV-infected subjects. The steady state exposures of RZR 180 mg in HCV subjects are anticipated to be similar to the clinical exposures achieved in the RZR thorough QT study, and expected to be well tolerated based on the preclinical and clinical exposures achieved to date in RZR program. The 180 mg dose was also chosen for this study because RZR exhibits less than dose-proportional PK over the 200 to 600 mg dose range; a dose greater than 180 mg is predicted to result in limited additional increase in RZR exposure. For detailed information, please refer to the RZR IB.

Taken together, the available data supported the evaluation of RZR in combination with MK-3682 as a highly efficacious 2-drug regimen, and this study PN041 (MK-3682 450 mg and RZR 180 mg) and the ongoing PN035 (MK-3682 450 mg and RZR 60 mg) will provide a robust dataset to further elucidate the dose response of RZR in combination with MK-3682 as a 2-drug regimen.

The single entity fit-for-purpose capsule formulation of RZR shows a moderate negative food effect, with a 50% decrease in C_{24hr} when co-administered with a high-fat meal. As such, in this study, subjects will be instructed to take study drugs on an empty stomach after an overnight fast, at least 1 hour before the morning meal. Drugs should be taken with water, but without food. A drug-drug interaction study with MK-3682 and RZR (MK-3682 PN008) showed no clinically significant drug interactions, thus supporting the coadministration of these drugs without need for dose adjustment.

4.2.5 Rationale for Endpoints

4.2.5.1 Efficacy Endpoints

The primary measurement for efficacy in this study is the plasma HCV RNA level. Long-term suppression of HCV RNA, typically reported as SVR, has been associated with improved outcomes in subjects with chronic HCV infection as measured by biochemical and histological remission of liver disease. Most available data suggest that SVR following antiviral therapy reduces the risk of progression to cirrhosis and may prevent the development of severe liver complications as well as improve survival [37].

The primary evaluation of efficacy in this trial is based on SVR_{12} , the same endpoint used for all investigational and approved DAAs. Since a high degree of concordance has been observed between SVR_{12} and SVR_{24} [38], SVR_{12} is now being used as the primary endpoint for registration of DAAs. A secondary evaluation of efficacy is based on SVR_{24} and for this study this will be a secondary endpoint [39].

4.2.5.1.1 Measurement of HCV RNA

HCV-RNA levels in plasma will be measured using the Roche COBAS® AmpliPrep/COBAS® TaqMan® HCV Test, v2.0 on blood samples drawn from each subject at various time points prior to, during, and after dosing, as indicated in the Trial Flow Chart (Section 6.0). Samples are collected and processed as per instructions provided by the manufacturer.

Results from the sample collected at the screening visit are used to determine eligibility. Samples collected at other time points, after Day 1, are used for efficacy analyses and to identify subjects who meet virologic failure criteria.

The nomenclature detailed in Table 5 will be used when describing HCV RNA levels:

Table 5 Nomenclature for Describing HCV RNA Levels

Abbreviation	Definition	HCV RNA Level
TND	Target not detected	HCV RNA not detected
TD(u)	Target detected but unquantifiable	HCV RNA <LLOQ
TD(q)	Target detected, quantifiable	HCV RNA ≥LLOQ

HCV = hepatitis C virus; LLOQ = lower limit of quantification; RNA = ribonucleic acid.

4.2.5.1.1.1 Definition of Efficacy Endpoints

Efficacy will be defined at different time points during the trial. Specific primary and secondary endpoints are:

- SVR₁₂: Subject has HCV RNA <LLOQ 12 weeks after the end of all study therapy.
- SVR₂₄: Subject has HCV RNA <LLOQ 24 weeks after the end of all study therapy.
- Virologic failure rate among subjects who do not discontinue the study for non-treatment-related reasons at FW12.

4.2.5.1.1.2 Definition of Virologic Failure: Non-Response, Rebound, Virologic Breakthrough and Relapse

Lack of efficacy at different time points in the trial will be categorized as:

- Non-response: Subject has HCV RNA detected at end of treatment without HCV RNA <LLOQ having been achieved while on treatment (note that breakthrough is distinguished below).
- Rebound: Subject has a rebound defined as >1 log₁₀ IU/mL increase in HCV RNA from nadir while on treatment and confirmed from a separate blood draw within 2 weeks.

- **Virologic breakthrough:** Subject has a confirmed HCV RNA \geq LLOQ (target detected, quantifiable [TD(q)]) after being $<$ LLOQ previously while on treatment. Confirmation is defined as an HCV RNA \geq LLOQ from a separate blood draw repeated within 2 weeks.
- **Relapse:** Subject has a confirmed HCV RNA \geq LLOQ [TD(q)] following end of all study therapy, after becoming undetectable (target not detected [TND]) at end of treatment. Confirmation is defined as an HCV RNA \geq LLOQ from a separate blood draw repeated within 2 weeks.

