5.11.4 Efficacy Criteria for Stopping Enrollment/Allocation

The efficacy criteria for stopping enrollment/treatment allocation are:

1. A total of ≥ 3 out of the first 10 subjects in the per-protocol (PP) population (see Section 8.5.1 for definition) for each GT (GT1-6) receiving 12 weeks of therapy experience virologic failure (non-response, rebound, breakthrough, or relapse) by FW4, or
2. >5 subjects in the PP population for GT1-4, and >3 subjects in the PP population for GT5-6, experience virologic failure at any point in the trial.

If either of these criteria is met, then no additional subjects of that particular GT would be allocated to treatment in the trial. Additionally, the Sponsor will review the results, and if the majority of failures are due to relapses (i.e., $>50\%$), the treatment regimen will be modified for all subjects of that GT still on treatment. If the treatment regimen is modified, the duration will be extended to 16 weeks and RBV will be added to the regimen (investigators will review considerations and contraindications to RBV with subjects impacted).

Criteria for HIV-infected Subjects

If a total of ≥ 2 HIV-infected subjects across all arms experience confirmed loss of HIV-1 virologic suppression at any time, then no additional HIV co-infected subjects will be enrolled. Loss of virologic suppression is defined as HIV-1 RNA ≥ 200 copies/mL, confirmed on 2 consecutive tests at least 2 weeks apart in subjects compliant with their HIV ARV therapies. Remaining co-infected subjects who are already on trial treatment will continue their assigned HCV treatment regimen while their HIV regimen is being reassessed.

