7.1.5.6 Discontinued Subjects Continuing to be Monitored in the Trial

Discontinuation During Treatment Period

Subjects who discontinue therapy in the trial prior to the last scheduled treatment visit should have an Early Discontinuation visit and then continue into follow-up visits.

At a minimum, the following information should be collected:

- The reason the subject discontinued
- The date of the last dose of study medications from the trial
- The date of the last assessment and/or contact. A follow-up contact (telephone or visit) will be arranged as appropriate
- (Serious) Adverse events (per reporting requirements outlined in Section 7.2)

Final assessments:

- Every effort should be made to ensure that all procedures and evaluations scheduled for the Early Discontinuation Visit are performed.
- Retrieve all study medications from the subject.

Discontinuation for Virologic Failure

Subjects who discontinue because they have met criteria for virologic failure (Section 4.2.5.1.1.2) while on study therapy should complete an Early Discontinuation Visit as outlined in the Trial Flow Chart (Section 6.0) and return to the study site for follow-up visits at 4, 8, 12, and 24 weeks following confirmation of virologic failure.

Subjects who meet the virologic failure criterion for relapse (HCV RNA \geq LLOQ following the end of all study therapy, after becoming undetectable [TND] at the end of treatment) will return to the study site for the remainder of their follow-up visits (e.g., 4, 8, 12, and 24 weeks) as outlined in the Trial Flow Chart (Section 6.0).

Discontinuation During Follow-Up Period

Subjects who discontinue during the follow-up period (e.g., follow-up visits at 4, 8, 12, and 24 weeks after end of treatment) for reasons other than virologic failure should complete an Early Discontinuation Visit as outlined in the Trial Flow Chart.

At a minimum, the following information should be collected:

- The reason the subject discontinued
- The date of the last assessment and/or contact. A follow-up contact (telephone or visit) will be arranged as appropriate
- SAEs (per reporting requirements outlined in Section 7.2)

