PP (Supportive for SVR ₁₂ and SVR ₂₄)	HCV RNA < LLOQ for baseline infection ¹ HCV RNA ≥ LLOQ demonstrated to be due to reinfection (detectable HCV RNA for a viral strain other than that detected at baseline after clearance of baseline infection ¹)	HCV RNA ≥ LLOQ for baseline infection ¹	Subject has important deviations from the protocol including discontinuation from the study for non-treatment related reasons and other violations such as violation of inclusion/exclusion criteria and use of prohibited concomitant medications (see Section 8.5.1)
mFAS (Supportive for SVR ₁₂ , SVR ₂₄ ; Primary for the proportion of subjects experiencing virologic failure at FW12)	HCV RNA < LLOQ for baseline infection ¹ HCV RNA ≥ LLOQ demonstrated to be due to reinfection (detectable HCV RNA for a viral strain other than that detected at baseline after clearance of baseline infection ¹)	HCV RNA ≥ LLOQ for baseline infection ¹	Subject discontinued from the study for non-treatment related reasons.
FAS = Full Analysis Set; FW12 = Follow-up Week 12; GT = genotype; LLOQ = lower limit of quantification; mFAS = modified Full Analysis Set; PP = Per Protocol; RNA = ribonucleic acid; SVR ₁₂ = sustained virologic response after 12 weeks of treatment; SVR ₂₄ = sustained virologic response after 24 weeks of treatment. ¹ Baseline infection: GT(s) and subtype(s) present at baseline based on sequencing and genotyping assay			

Subject Virologic Failure: Non-response, Rebound, Virologic Breakthrough, Relapse and Reinfection

Summary statistics will be provided to describe the rates of occurrence of subject non-response, rebound, virologic breakthrough, and relapse. Definitions for subject non-response, rebound, virologic breakthrough, and relapse are in Section 4.2.5.1.1.2. Reinfection will be defined as having detectable virus of a different GT than that detected at baseline as determined by sequencing. Those with reinfection will be considered treatment success in the mFAS and PP analyses as long as HCV RNA < LLOQ is achieved for the baseline infection.

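### Relapse requires target-not-detected at end of treatment, so a confirmed recurrence from detectable but unquantifiable RNA has no failure category, and the documents disagree on whether it counts at FW12

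*Combined protocol and SAP*

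**What the plan says.** Table 5 in Section 4.2.5.1.1 has three states: target not detected (TND); TD(u), described as "Target detected but unquantifiable" and lying below the LLOQ; and TD(q), at or above the LLOQ.

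Section 4.2.5.1.1.2 then gives four failure categories:

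- Non-response: "Subject has HCV RNA detected at end of treatment without HCV RNA <LLOQ having been achieved while on treatment".
- Rebound: a rise of more than 1 log10, specified as an "increase in HCV RNA from nadir while on treatment and confirmed from a separate blood draw within 2 weeks".
- Breakthrough: a confirmed result at or above the LLOQ in a subject who had earlier been below it, with the on-treatment qualifier at the end of the sentence.
- Relapse: a confirmed result at or above the LLOQ after all therapy, "after becoming undetectable (target not detected [TND]) at end of treatment".

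Section 7.1.5.6 repeats the relapse condition: "after becoming undetectable [TND] at the end of treatment".

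Stopping rule 1 in Section 5.11.4 counts subjects who "experience virologic failure (non-response, rebound, breakthrough, or relapse) by FW4". Rule 2 uses the term virologic failure without a list. Section 8.7 repeats both rules, together with the test of whether more than 50% of failures are relapses. Section 8.6.1 refers back for its category summaries: "Definitions for subject non-response, rebound, virologic breakthrough, and relapse are in Section 4.2.5.1.1.2". Sections 3.2 and 8.4.1.1 describe the secondary endpoint as on-treatment failure or post-treatment relapse.

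**The concern.** Relapse is the only post-treatment failure category, and it is stricter than the definitions around it. SVR12, SVR24 and the exploratory end-of-treatment response in Section 8.4.1.3 all use the LLOQ, and Section 8.4.1.3 expressly accepts TD(u). A subject can therefore be an end-of-treatment responder and an SVR12 failure without belonging to any virologic-failure category.

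Four uses depend on the categories: the two efficacy stopping rules, the more-than-50%-relapses test, the failure summaries in Section 8.6.1, and resistance assessment. Section 4.2.5.1.2 limits resistance assessment to subjects above 1000 IU/mL who have met a failure criterion, apart from a separate provision for early discontinuations. The thresholds are small counts (3 of 10, more than 5, more than 3), so one unclassified subject can decide the result.

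**Working it through.** **1. Which patterns have a category?** Breakthrough is read here as on-therapy, and a quantifiable end-of-treatment (EOT) result is taken as confirmed.

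| Below LLOQ on treatment? | EOT state | After treatment | Category |
|---|---|---|---|
| Yes | TND | confirmed ≥LLOQ | relapse |
| Yes | TD(u) | confirmed ≥LLOQ | none |
| Yes | TD(q) | either | breakthrough |
| No | TD(q) | either | non-response |

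A subject who is TD(u) at EOT is by definition below the LLOQ on treatment, so the condition "without HCV RNA <LLOQ having been achieved while on treatment" rules out non-response. Without an on-treatment rise there is no rebound. The TD(u) row is the only post-treatment recurrence left without a category.

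**2. FW12 virologic-failure endpoint.** Sections 3.2 and 8.4.1.1, read with Section 4.2.5.1.1.2, leave this subject out. Section 8.6.1 says Table 16 gives the criteria for this endpoint. The mFAS row of Table 16, marked primary for it, sets non-response as HCV RNA at or above the LLOQ for the baseline infection, with no EOT condition. That counts a subject who is at or above the LLOQ at FW12. Table 16 does not cover every case. Under TRD=F, a subject who leaves for a non-treatment reason stays a failure only if virologic failure is documented. A TD(u) subject who recurs at FW4 and then leaves could therefore be excluded.

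**3. Size on the endpoint.** The plan's interval reproduces: Clopper-Pearson for 47/50 gives 94.0% (83.5, 98.7), as in Table 18. The complement is 3/50 = 6.0% (1.3, 16.5). With one subject uncounted it becomes 2/50 = 4.0% (0.5, 13.7). One subject is 1/50 = 2 points, or 1/25 = 4 points in GT5 or GT6.

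**4. One subject can decide a rule (illustrations).**

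- First 10 subjects with 1 breakthrough, 1 relapse from TND and 1 recurrence from TD(u): the text counts 2/10, rule 1 not met. Counting all gives 3/10, met, with 2/3 = 67% post-treatment recurrences.
- 2 breakthroughs and 2 relapses: 2/4 = 50%, so the more-than-50% test is not met. Adding one uncounted recurrence gives 3/5 = 60%, met.

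**5. Chance of meeting each rule.** Let p be the true failure rate and q the share of failures left uncounted. The documents do not give q; 0 to 30% is assumed, with all failures being relapses. The counted rate is p(1−q), for example 0.30 × 0.90 = 0.27. The entries are exact binomial tails, P(X≥3) for n=10 and P(X≥6) for n=50.

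| Rule | p | q=0 | 5% | 10% | 30% |
|---|---|---|---|---|---|
| ≥3 of 10 | 30% | 61.7% | 57.6% | 53.4% | 35.3% |
| >5 of 50 | 15% | 78.1% | 73.5% | 68.4% | 43.0% |
| >5 of 50 | 30% | 99.9% | 99.9% | 99.7% | 96.6% |

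**6. What the documents suggest about q.** Section 4.1.2.2.1.2 (three-drug regimen) reports all GT1 and all GT3 subjects undetectable at EOT. Of 283 GT3 subjects, 276 achieved SVR4, leaving 7 without it. If undetectable means TND, 0 of those 7 came from TD(u). The Clopper-Pearson upper limit for 0/7 is 1 − 0.025^(1/7) = 41%, so these data favour a low q without excluding the assumed range. GT2 is reported only as 134/135 below the LLOQ.

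**The case against.** **The endpoint.** A reader might infer that the FW12 virologic-failure analysis simply misses this subject. Table 16 contradicts that, so the supportable statement is that the sections conflict, with a remaining gap for subjects who leave before FW12.

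**Breakthrough.** Read literally, the on-treatment qualifier can attach to the earlier result below the LLOQ, and breakthrough would then cover this subject. It would also absorb every relapse. Footnote 14 of the flow chart treats breakthrough as failure during therapy, and Table 11 makes it a reason to stop treatment. The on-therapy reading is the better one, but the wording is ambiguous.

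**Frequency.** The three-drug data point to a low q, and in PN035, with the same two drugs, no breakthroughs had been seen among 122 subjects who had started treatment. That makes the two-breakthrough illustration less likely. This stands, with limits: the first source is another regimen, PN035 was still dosing, and Section 4.1.2.2.2 writes undetectable where its Table 4 is headed below 15 IU/mL, so the terms are not always kept apart.

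**Binomial figures.** They take each rule alone, although either one suffices. They run rule 2 to a full genotype group, when stopping allocation no longer changes anything. At a 30% failure rate rule 2 barely moves. These points stand, and the figures are illustrative.

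**Oversight.** The trial is open-label, and Section 8.7 also provides for general monitoring of efficacy trends, so the sponsor would see such a result. That softens the undercount but does not repair the numerical rules.

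**Conclusion.** The gap holds on the on-therapy reading of breakthrough. As written, a subject who is TD(u) at end of treatment and confirmed at or above the LLOQ afterwards is not counted by the stopping rules, the more-than-50%-relapses test or the category summaries. A treatment completer in this position also does not meet the failure criterion for resistance assessment. For the FW12 endpoint the documents give two answers for the same subject.

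The documents do not support reading this as a flaw in the primary result. SVR12 in the FAS with M=F depends only on the LLOQ at FW12, whatever the end-of-treatment state. Nor is a test's error rate at stake, because the trial is for estimation only.

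The size cannot be fixed from the documents. If q is near zero the effect is negligible. At q=10%, rule 1 at a 30% failure rate loses 61.7 − 53.4 = 8.3 points, and rule 2 at 15% loses 78.1 − 68.4 = 9.7 points. Both figures assume that all failures are relapses. The definition should be settled because a single subject can decide a rule.

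**What to change.** For the virologic-failure endpoint and the category summaries in Section 8.6.1, classify as virologic failure (relapse) any confirmed HCV RNA at or above the LLOQ after the end of all study therapy in a subject who was below the LLOQ at end of treatment, whether TND or TD(u). Keep the existing reinfection provision for the mFAS and PP analyses. This agrees with Table 16, and it makes a recurrence before an unrelated withdrawal a documented failure under TRD=F.

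Reconcile Sections 4.2.5.1.1.2, 5.11.4, 7.1.5.6, 8.4.1.1, 8.6.1 (with Table 16) and 8.7 so that one definition of virologic failure is used throughout, and state explicitly that breakthrough is an on-therapy event if that is intended. The sponsor should decide and record how the definition applies to the stopping and regimen-modification rules; no clinical rule is proposed here.

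The cost is a wording change with no new data. Section 8.0 allows the analysis part to be documented in the supplemental SAP before database lock. The reported virologic-failure rate may rise slightly.
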